7.1.4 Compatibility

Not applicable

7.1.5 Handling

Qualified personnel, familiar with procedures that minimize undue exposure to themselves and the environment, should undertake the preparation, handling, and safe disposal of the chemotherapeutic agent in a self-contained and protective environment. Avoid contact with broken tablets.

7.1.6 Availability

Everolimus will be supplied free of charge by Novartis for this study.

7.1.7 Preparation

Everolimus will be made available in blister packs of tablets. No specific preparation will be required

7.1.8 Administration

Everolimus is taken orally once daily.

7.1.9 Ordering

Drug supply will be ordered by pharmacy personnel at each site using the Drug Request Form in Appendix B.

7.1.10 Accountability

The investigator, or a responsible party designated by the investigator, must maintain a careful record of the inventory and disposition of the agent (investigational or free of charge) using the NCI Drug Accountability Record or another comparable drug accountability form. (See the CTEP website at <http://ctep.cancer.gov/protocolDevelopment> for the “Policy and Guidelines for Accountability and Storage of Investigational Agents” or to obtain a copy of the drug accountability form.)

7.1.11 Destruction and Return

At the end of the study, unused supplies of everolimus should be destroyed according to institutional policies. Destruction will be documented in the Drug Accountability Record Form.

8. CORRELATIVE/SPECIAL STUDIES

8.1 Pharmacokinetic Studies

As everolimus is an approved agent, no pharmacokinetic studies will be performed.

8.2 Pharmacodynamic Studies

8.2.1 Laboratory Correlative Studies

8.2.1.1 Whole exome sequence analysis of tumor specimen

Paraffin blocks of tumor biopsies or resection specimens will be collected at the time of study entry by the Principal Investigator for whole exome sequencing analysis. If paraffin blocks are not released by the pathology department, unstained slides maximum of 20 and minimum of 5 will be requested with each tissue cut measuring a minimum of 4 microns in width. These samples will be sent to the research laboratory of the Principal Investigator at the following address: [name], Brigham and Women’s Hospital, [name]. These samples will be used for DNA extraction and analysis by whole exome sequencing at the Broad Institute. A paired normal DNA sample is required

13-March-2017

for this analysis and will be collected as a blood sample on the date of study entry. Whole exome data will be analyzed using standard pipeline tools in use at the Broad Institute, including Mutect to identify sequence variants present in the cancer and not in the normal DNA sample, and CapSeg to identify regions of significant copy number variation across the genome.

9. STUDY CALENDAR

Baseline evaluations are to be conducted within 1-week prior to start of protocol therapy. Scans must be done ≤ 4 weeks prior to the start of therapy. In the event that the participant's condition is deteriorating, laboratory evaluations should be repeated within 48 hours prior to initiation of the next cycle of therapy.

All assessments must be performed prior to administration of any study medication. All study assessments and medications should be administered within **one week** of the protocol-specified date, unless otherwise noted.

Action	Study entry (within 14 days of day 1 unless otherwise noted))	Day1	At clinic visit every 4 weeks* (This may be extended to every 8 weeks after cycle 2 upon investigator's discretion)	Every 8 weeks for max. 24 months*	End of Study
Informed consent	X (within 28 days of day1)				
Medical history and height	X				
Inclusion/exclusion criteria	X				
Vital Signs	X	X	X		X
ECOG Performance status	X	X	X		X
Physical examination and weight	X	X	X		X
AE's and con- medications/treatments	X	X	X		X
Pregnancy test (female subjects <50)	X (in clinic)	X	X (in clinic)	X**	
Hematology and blood chemistry	X	X***	X		X
Urinalysis	X	X (only if abnormal at baseline or clinically indicated)			
CT/MRI chest, abdomen, and other disease sites, as appropriate	X (within 30 days of day 1)			Repeat scans of areas of known disease or of new areas based on clinical judgment	
Everolimus	Administered daily continuously until removal from study				
Cf-DNA blood		X			
Archived tumor sample	Sample must have been acquired no longer than 2 years prior to enrollment in the study				
Tumor biopsy	Participants who achieved either a partial response or stable disease \geq 4 months must agree to a tumor biopsy upon disease progression, assuming it is judged safe and feasible by treating physician				

- +/- one week depending on appointment availability due to holidays or unforeseen events
- **When women of child-bearing age are being seen every two months, it is recommended that they perform home pregnancy testing at 1 month between visits. They should also have an office pregnancy test at every visit. Patients will be contacted by a member of the study team via phone to track the pregnancy tests performed at home.
- ***Hematology and blood chemistry studies need to be assessed on C1D1 only if screening was performed >72 hours prior. In this case laboratory values on cycle 1 day 1 must meet eligibility criteria.

Hematology: hemoglobin, hematocrit, platelets, total white blood cell count (WBC) and differential.

Chemistry: must include sodium, potassium, chloride, bicarbonate, calcium, glucose, creatinine, blood urea nitrogen, albumin, total protein, SGOT (AST), SGPT (ALT), total bilirubin, alkaline phosphatase, uric acid, phosphorus, serum lipid profile (triglycerides, total cholesterol, HDL and LDL). *Because accurate serum glucose and lipid measurements are required, patients should be fasting at the time of the blood sampling.*

Urinalysis: Standard urinalysis dipstick assessment (pH, protein, glucose, blood, ketones, and leukocytes) should be performed at baseline. This must be supplemented with laboratory quantification of any potentially relevant abnormalities.

Physical Examination: General appearance, skin, head, neck, lungs, heart, abdomen, lymph nodes, extremities and basic nervous system.

cf-DNA blood: to be collected pre-dose on day 1 of cycle 1 using Cell- Free DNA BCT (Sterck) tube, 10ml or PAXgene, DNA tubes 8.5 ml . Store at room temperature (ambient) for same day shipment

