Several clinical studies have now been reported in which everolimus has shown clinical benefit for patients with cancers with mutations in TSC1 or TSC2. Randomized clinical trials in patients with the genetic disorder Tuberous Sclerosis Complex (TSC) who have tumors in the brain, subependymal giant cell astrocytoma, or renal angiomyolipoma, have shown benefit in response to everolimus treatment (7, 8). PEComas, a sarcoma related to angiomyolipoma, but occurring in non-TSC patients and usually due to mutations in TSC2, have also shown benefit including sustained complete responses while on everolimus (9, 10). Finally, a recent report described a clinical trial of everolimus for bladder cancer, in which one patient had a sustained complete clinical response lasting over 2 years (11). That patient was shown to have a TSC1 inactivating mutation in her cancer. Notably, other bladder cancer patients on that trial whose cancers also had mutations in TSC1 had transient minor responses. However, the majority of patients on the trial had no mutations in TSC1, and showed progressive disease. Both TSC1 and TSC2 mutations and mTOR activating mutations have been identified in a set of 6 extreme responders to Everolimus out of 300 patients with renal cell carcinoma treated at Memorial Sloan Kettering (12). Furthermore, an activating MTOR mutation has been associated with exceptional response to treatment

in a bladder cancer patient (13), and multiple, relatively common, activating MTOR mutations have been defined through in vitro studies (14).

We hypothesize that due to the positioning of TSC1/TSC2 as a key regulator of mTORC1, that all cancers with inactivating mutations in TSC1 or TSC2 will have sensitivity to everolimus. The extent of sensitivity will likely depend on other genomic events present in these cancers, tissue type, and other unknown factors. Furthermore, we similarly hypothesize that cancers bearing MTOR activating mutations will also have sensitivity to everolimus.

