5.3 Pretreatment Criteria

The first dose of Everolimus may be administered on the same day as enrollment but no more than 10 business days after enrollment. The treatment period begins on the first day of treatment with Everolimus.

If a subject is unable to come into the clinic for a required study visit or if unforeseen events occur, the visit procedures may be performed within a one week time frame.

The following assessments will be performed at each clinic visit according to table 3.4 throughout the treatment period:

- Physical examination,
- ECOG performance status,
- Blood pressure, respiratory rate, resting pulse, temperature, and weight.
- Laboratory evaluations: If patients have met trial eligibility within the previous 72 hours, no specific criteria will need required in order to initiate the protocol unless, in the investigator's opinion, significant medical issues arise which would contraindicate starting the study medications. If patients have completed entry criteria >72 hours prior to cycle 1 day 1, laboratory values on cycle 1 day 1 should be repeated to confirm all eligibility criteria are met.
- CT scans (contrast-enhanced) or MRI scan (contrast-enhanced) or PET-CT scan of areas of known disease every 8 weeks with a 5 business-day time window in case unforeseen events occur. Evaluation according to RECIST criteria compared to previous scan.
- beta HCG pregnancy test for women of child-bearing potential

Documentation of all adverse events will occur at each clinic visit and at any other time point when necessary. There are no specific criteria for the initiation of a given cycle except for the ones indicated in the dose modification tables 6-2, 6-3 & 6-4. Study subjects may commence with treatment if, in the opinion of the investigator and based on the guidance of Section 6, it is safe for the participant to do so.

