5.6 Duration of Therapy

Duration of therapy will depend on individual response, evidence of disease progression and tolerance. In the absence of treatment delays due to adverse events, treatment may continue forever or until one of the following criteria applies:

- Disease progression,
- Intercurrent illness that prevents further administration of treatment,
- Unacceptable adverse event(s),
- Participant demonstrates an inability or unwillingness to comply with the oral medication regimen and/or documentation requirements
- Participant decides to withdraw from treatment but is willing to be followed,
- Participants decides to withdraw consent from the study, or
- General or specific changes in the participant's condition render the participant unacceptable for further treatment in the opinion of the treating investigator.

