10. MEASUREMENT OF EFFECT

For the purposes of this study, participants should be re-evaluated for response every 8 weeks. In addition to a baseline scan, confirmatory scans should also be obtained 4-

13-March-2017

8 weeks (not less than 4 weeks) following initial documentation of objective response.

Response and progression will be evaluated in this study using the new international criteria proposed by the Response Evaluation Criteria in Solid Tumors (RECIST) 1.1 (Eisenhauer et al., 2009). Changes in the diameter (unidimensional measurement) of the tumor lesions are used in the RECIST 1.1 criteria.

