10.1.6 Progression-Free Survival

Progression-Free Survival (PFS) is defined as the duration of time from study registration to the date of documented disease progression or death, whichever occurs first. Patients not experiencing an event will be censored at the date of the last disease assessment.

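### The calendar limits scheduled scans to 24 months while treatment and 8-weekly assessment are open-ended elsewhere; if the calendar governs, the late PFS curve is biased downward

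*Combined protocol and SAP*

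**What the plan says.** The calendar in section 9 places on-study CT/MRI in one column only, headed "Every 8 weeks for max. 24 months". The entry reads "Repeat scans of areas of known disease or of new areas based on clinical judgment". The asterisk adds a one-week tolerance and nothing more, and the End of Study column has no scan. In the same table everolimus is "Administered daily continuously until removal from study", and section 5.6 says "treatment may continue forever or until one of the following criteria applies".

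Two sections give an assessment schedule with no end. Section 5.3, for the treatment period, calls for imaging "of areas of known disease every 8 weeks with a 5 business-day time window". Section 10 says "participants should be re-evaluated for response every 8 weeks". Section 6.2.1.6 also mentions scans every 8 weeks but refers back to the schedule of events, that is, to the calendar.

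For the analysis, PFS ends at documented progression or at death from any cause (sections 10.1.6 and 14.1). Otherwise, "Patients not experiencing an event will be censored at the date of the last disease assessment". Duration of response ends only when recurrence or progression is documented (sections 10.1.5 and 14.1). Section 14.1 plans Kaplan-Meier medians, 6-month and 1-year estimates with 90% confidence intervals. Section 5.7 follows patients to death by record review and contact every 3 months and mentions no scans.

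**The concern.** A site that stops scheduled scans at month 24 and a site that continues them can both claim to follow the protocol. If the calendar governs, a patient may remain on drug after month 24 with no scan planned, although section 5.6 lists progression among the reasons to stop.

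The analysis consequence comes from treating survivors and deaths differently. An event-free survivor with no further assessment leaves the PFS risk set near month 24. A similar patient who dies later stays in the risk set until death and is then counted as an event. After month 24 the risk set is therefore made up largely of patients selected because they died.

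Long disease control is a realistic outcome here. The rationale in section 2.2 cites an earlier everolimus trial in which "one patient had a sustained complete clinical response lasting over 2 years". These are the patients for whom the two schedules differ.

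**Working it through.** The plan states no figure for PFS or duration of response, so there is nothing to reproduce. The check has four parts.

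**1. What the calendar provides.** 24 months is 24 × 365.25 / 12 / 7 = 104.4 weeks. Divided by 8 this is 13.04, so about 13 on-study scans, the last near week 104. Sections 5.3 and 10 set no last scan.

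**2. How many patients are affected.** The documents give no median PFS, so I assume exponential times over a range of medians: S(24) = 0.5^(24/median). Section 14.3 plans 30 patients, while section 14.1 describes 50 + 10 = 60. That is a separate inconsistency, so both counts are shown.

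| Assumed median PFS (months) | Progression-free at 24 months | Of 30 | Of 60 |
|---|---|---|---|
| 6 | 0.5^4 = 6% | 1.9 | 3.8 |
| 12 | 0.5^2 = 25% | 7.5 | 15.0 |
| 18 | 0.5^1.333 = 40% | 11.9 | 23.8 |
| 24 | 0.5^1 = 50% | 15.0 | 30.0 |

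**3. Direction of the PFS effect.** Take an invented example. Of 30 patients, 7 are event-free at 24 months and none is scanned again. Five stay alive and are censored there; two die, at months 30 and 36.

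- At 24 months: 7/30 = 0.233.
- At month 30, two at risk and one death: 0.233 × 1/2 = 0.117.
- At month 36, one at risk and one death: 0.117 × 0 = 0.

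The curve reaches zero with five of the seven alive and no progression known. Had those five been assessed throughout and stayed event-free, the curve would end at 5/30 = 0.167.

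**4. Ceiling on duration of response.** Suppose response is first seen at the week-8 scan (1.84 months). Section 10.1.5 starts the clock when response criteria are first met, which leaves 24 − 1.84 = 22.2 months of scheduled scanning. Section 14.1 refers to confirmed response, and section 10 puts the confirmatory scan 4 to 8 weeks later. If the clock starts at confirmation, the ceiling is 24 − 2.76 = 21.2 to 24 − 3.68 = 20.3 months. Later responses shorten it further. The share of responders whose duration exceeds the ceiling, again assuming exponential times, is 0.5^(ceiling/median):

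| Assumed median duration (months) | Ceiling 22.2 | Ceiling 20.3 |
|---|---|---|
| 6 | 8% | 10% |
| 12 | 28% | 31% |
| 18 | 43% | 46% |
| 24 | 53% | 56% |

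Only in the last row is the median itself out of reach. With 30 patients and an assumed 30% response rate there are 9 responders. Rounding the ceiling to 22 months, about 0.7, 2.5 and 4.8 of them are still in response at month 24 for median durations of 6, 12 and 24 months.

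**Effect on planned summaries.** The 6-month and 1-year estimates lie before month 24 and do not change. Median PFS changes only if the curve is still above 50% at month 24. The upper confidence limit of the median can be drawn in somewhat sooner. With 30 patients, no earlier censoring and a linear Greenwood interval, a true median of 18 months gives an upper 90% bound on S(24) of 0.397 + 1.645 × √(0.397 × 0.603 / 30) = 0.54, above one half. For a median of 12 months the bound is 0.25 + 1.645 × √(0.25 × 0.75 / 30) = 0.38, and the limit falls before month 24.

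**The case against.** A reader might infer that after month 24 PFS and duration of response can end only through death or unscheduled imaging. The documents do not support that, for three reasons.

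- It assumes that the calendar overrides sections 5.3 and 10. No passage says so, and those sections still ask for 8-weekly assessment. The calendar column also carries a pregnancy-test entry, so its heading is not plainly a rule for stopping scans.
- Death does not end duration of response under either definition, so the mixture of censored survivors and late deaths concerns PFS alone. How a death without documented progression is handled for duration of response is a separate gap.
- Clinic visits with physical examination have no 24-month limit, and section 10.1.3 accepts superficial lesions measured clinically, so some progression could still be documented without a scan.

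Nor do the documents support the reading that long responders are the purpose of the trial. The primary objective is objective response; PFS and duration of response are secondary, and the long response cited in section 2.2 is one patient. Treatment is also not strictly tied to progression on a scan, because section 5 allows it to continue beyond progression with PI approval.

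A further objection is that a common PFS cut-off changes the stated endpoint. It drops a death soon after the last scan and a progression found later by prompted imaging. That cost is real, and choosing a single schedule may make a cut-off unnecessary.

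These arguments make the consequence conditional and narrow its reach. They do not remove the contradiction or tell the analyst what to do after the last scheduled scan.

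**Conclusion.** The contradiction stands: one section limits scheduled scans to 24 months, two set no limit, treatment is open-ended, and no passage ranks them. If the calendar governs, the stated PFS rule biases the late curve downward, and scheduled scans can follow a response for at most about 20 to 22 months.

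The reach is modest. It covers secondary endpoints in patients event-free at 24 months, a share that runs from 6% to 50% as the assumed median PFS runs from 6 to 24 months. That range rests on exponential times and on medians the documents do not give. At the short end about 2 of 30 patients are involved and no planned PFS summary moves. The primary response rate is little affected. This is a minor point, worth correcting because the correction is cheap.

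**What to change.** Reconcile the calendar with sections 5.3, 5.6, 6.2.1.6 and 10 so that one assessment schedule applies for as long as patients are treated. This review does not say which schedule is right.

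If a scan limit is kept, add to section 14.1:

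- one common PFS cut-off tied to the end of scheduled assessment, for example the month-24 scan plus its window, applied equally to survivors and to later deaths. The window must itself be settled, since section 5.3 gives 5 business days and the calendar one week;
- the present definition, with all deaths counted, as a sensitivity analysis;
- duration of response censored at the last disease assessment.

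The cost is a protocol wording change and a few sentences in section 14.1, and the analysis change needs no extra scans. The downside is that events after the cut-off leave the main PFS analysis; the sensitivity analysis still counts them. Overall survival is unchanged.

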10. MEASUREMENT OF EFFECT

For the purposes of this study, participants should be re-evaluated for response every 8 weeks. In addition to a baseline scan, confirmatory scans should also be obtained 4-

13-March-2017

8 weeks (not less than 4 weeks) following initial documentation of objective response.

Response and progression will be evaluated in this study using the new international criteria proposed by the Response Evaluation Criteria in Solid Tumors (RECIST) 1.1 (Eisenhauer et al., 2009). Changes in the diameter (unidimensional measurement) of the tumor lesions are used in the RECIST 1.1 criteria.

10.1.1 Definitions

Evaluable for toxicity: All participants who receive at least one dose of study treatment will be evaluable for toxicity from the time of their first treatment.

Evaluable for objective response: Only those participants who have measurable disease present at baseline, have received at least one cycle of therapy, and have had their disease re-evaluated will be considered evaluable for response. These participants will have their response classified according to the definitions stated below. (Note: Participants who exhibit objective disease progression or die prior to the end of cycle 1 will also be considered evaluable.)

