5.7 Duration of Follow Up

Participants will be followed until death after removal from treatment. This follow-up will be performed by review of the medical record, contact with care providers, and/or telephone contact as needed every 3 months.

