14.1 Study Design/Endpoints

The primary objective of this trial is objective response rate according to RECIST 1.1 criteria.

Secondary objectives include duration of response, progression-free and overall survival. Duration of response is defined as the time from RECIST-confirmed response (CR+PR) to documented disease progression. Progression-free survival is defined as the time from study registration to documented disease progression per RECIST 1.1 or death from any cause, whichever occurs first. Patients not experiencing a PFS event will be censored at the date of their last disease assessment. Overall survival is defined as time from registration to death from any cause, censoring patients thought to be alive at the time of final analysis at the last date of follow up. We will also estimate toxicity via CTCAE version 4.0, and the association of IHC and whole exome sequencing results with patient outcomes and other genetic events.

We will estimate event-time distributions using the Kaplan-Meier method, using Greenwood's formula to estimate the variance and provide 90% confidence intervals for the medians, 6-month, and 1-year estimates. Categorical outcomes, such as toxicity and response, will be estimated and their corresponding 90% exact binomial confidence intervals will be provided.

For the cohort of patients with TSC1 and TSC2 mutations, we will conduct this study using a Simon's two-stage design. In the first stage we will enroll 21 patients and if a total of at least 4 responses (CR + PR) are observed among them, accrual to the second stage will open. If 3 or fewer responses are observed among the first 21 patients, the study will terminate. In the second stage, an additional 29 patients will be enrolled for a total study accrual of 50 patients. After accrual to the second stage is completed, we will declare study success if at least 8 responses are observed among the 50 registered patients. This design has a probability of stopping early after the first stage of accrual of 85% if the drug is ineffective; the overall power of the study to detect the targeted response rate of 30% (compared to a null of 10%) is 91% while controlling the type I error at a one-sided level of 0.07.

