For the cohort of 10 patients harboring mTOR mutations, we are somewhat limited in the inferences that can be made, however we would consider observing at least 2 responses in this cohort worthy of additional study. The maximum half-width of the 90% exact binomial confidence interval will be 23.5%.

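### Section 10.1.1 drops some treated patients who cannot be responders from the response-evaluable set, and Section 14.1 names no population for the reported response rate and its 90% exact interval

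*Combined protocol and SAP*

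**What the plan says.** Section 10.1.1 sets three conditions for being evaluable for objective response. Patients must have measurable disease at baseline, and only those who also "have received at least one cycle of therapy, and have had their disease re-evaluated will be considered evaluable for response". A note adds one exception: "Participants who exhibit objective disease progression or die prior to the end of cycle 1 will also be considered evaluable".

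Section 10 sets the assessment interval: "participants should be re-evaluated for response every 8 weeks". Section 5.1 defines a cycle as 28 days, so the first planned rescan falls at the end of cycle 2.

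Section 5.6 foresees stopping for adverse events, intercurrent illness or a change in condition, and also lists "Participant decides to withdraw from treatment but is willing to be followed". After treatment ends, Section 5.7 describes survival-type follow-up with no scheduled scan: "This follow-up will be performed by review of the medical record, contact with care providers, and/or telephone contact as needed every 3 months".

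Section 14.1 states the final rule for the TSC1/TSC2 cohort on registered patients: "we will declare study success if at least 8 responses are observed among the 50 registered patients". The stage 1 rule refers to the first 21 patients and the MTOR rule to a cohort of 10. For estimation, Section 14.1 says only: "Categorical outcomes, such as toxicity and response, will be estimated and their corresponding 90% exact binomial confidence intervals will be provided". That sentence names no population, and Section 14 nowhere refers to the evaluable set of Section 10.1.1.

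**The concern.** The plan contains two candidate denominators for its primary estimate and does not say which one applies. An analyst could divide by the Section 10.1.1 set or by the registered patients of Section 14.1, and claim to have followed the protocol either way.

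The choice matters because the exclusion is related to outcome. A patient with no post-baseline scan cannot have a RECIST response. Removing such patients leaves the numerator alone and shrinks the denominator, so the reported rate can only rise. Stopping early for toxicity or deterioration is plausible in a population with advanced cancer, ECOG status up to 2 and any number of prior therapies. The published rate would then describe a more favourable group than the one on which success was declared.

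**Working it through.** **Who is excluded.** Compare Section 10.1.1 with the 8-week scan interval and the follow-up in Section 5.7.

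| Treated patient | In the 10.1.1 set? | Can be a responder? |
|---|---|---|
| Dies, or has objective progression, before day 28 | Yes (note) | No |
| Stops for toxicity, withdrawal or clinical deterioration, never rescanned | No | No |
| Dies after cycle 1, before any scan | No | No |
| Stops within cycle 1, rescanned later | No (less than one cycle) | Possible |

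The second and third rows carry the one-way bias. In the fourth row the direction is not fixed. Registered patients who are never treated do not add to the problem, because Sections 4.1 and 4.3 cancel their registration.

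**The plan's own design figures.** Inputs from Section 14.1: 21 patients in stage 1, stop at 3 or fewer responses, 50 in total, success at 8 or more, null 10%, target 30%.

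- Early stopping = P(X₁ ≤ 3 | 21, p). At p = 0.10 this is 0.848 (stated 85%).
- Success probability = Σ over x₁ ≥ 4 of P(X₁ = x₁ | 21, p) · P(X₂ ≥ 8 − x₁ | 29, p). At p = 0.10 this is 0.066 (stated 0.07). At p = 0.30 it is 0.912 (stated 91%).

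All three reproduce. They rest on counts among registered patients, so the choice of denominator for the reported rate does not touch them.

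**Which denominator Section 14.1 seems to have in mind.** The plan gives one numerical interval width, for the MTOR cohort: "The maximum half-width of the 90% exact binomial confidence interval will be 23.5" percent. The 90% Clopper-Pearson interval for 2/10 is 3.68% to 50.69%, and (50.69 − 3.68)/2 = 23.5. For 2/8 it is 4.64% to 59.97%, half-width 27.7. The stated figure fits 2 responses on the full cohort of 10. It is not the maximum over all outcomes, since 5/10 gives 27.8, so the match supports the full-cohort reading without proving it.

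**Size of the effect.** With x responses, N registered and treated patients, and k excluded patients who are not responders, the rate becomes x/(N − k) = (x/N) · N/(N − k). The documents give no non-evaluable share, so k is assumed. N = 50 is the Section 14.1 cohort; x = 8 is the success boundary. Intervals are 90% Clopper-Pearson.

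| Cohort | k assumed | Rate | 90% exact interval |
|---|---|---|---|
| TSC1/TSC2 | 0 | 8/50 = 16.0% | 8.2 to 27.0 |
| TSC1/TSC2 | 5 (10%) | 8/45 = 17.8% | 9.2 to 29.8 |
| TSC1/TSC2 | 10 (20%) | 8/40 = 20.0% | 10.4 to 33.2 |
| MTOR | 0 | 2/10 = 20.0% | 3.7 to 50.7 |
| MTOR | 2 (20%) | 2/8 = 25.0% | 4.6 to 60.0 |

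The relative inflation is 50/45 = 1.11 at 10% excluded. At 20% it is 1.25 (50/40 and 10/8).

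**The case against.** The strongest reply is that Section 14.1 already answers the question. Every efficacy statement there refers to a full cohort (the first 21, the 50 registered, the cohort of 10), its one interval width fits 2/10, and Section 14 never uses the term evaluable. Section 10.1.1 sits under measurement of effect and says whose response is classified; it does not say that the rate is computed on that set. On this reading only a cross-reference is missing.

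Much of that stands, and it is why the point is minor. It does not close the gap: no section says that the estimate disregards the evaluable set, or that unassessed patients count as non-responders. Section 10.1.4.1 assigns an unknown category when target-lesion data are missing, but does not say how a patient with no scan enters the rate.

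It is also fair that the excluded group is limited. A reader might infer that every patient who is never rescanned is dropped. The documents do not support that, because the note keeps deaths before the end of cycle 1. Section 10.1.4.3 also asks sites to try to document progression after treatment stops, which shrinks the group further without removing it.

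**Conclusion.** The point holds as a minor defect in the definition of the primary estimate. Taken literally, Section 10.1.1 excludes some treated patients who cannot be responders, and Section 14.1 does not prevent that set from being used for the response rate and its interval. If it is used, the estimate is biased upward by these patients and does not match the decision-rule population. At the success boundary the shift is 1.8 percentage points with 5 of 50 excluded (17.8 − 16.0) and 4.0 points with 10 excluded (20.0 − 16.0).

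Two stronger readings are tempting, and the documents support neither:

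- **An inflated error rate.** Success is a count of responses among registered patients, and its type I error (0.066) and power (0.912) stand as written.
- **A changed conclusion.** With 10 excluded, the lower limit for eight responses moves from 8.2% to 10.4%, past the 10% null. No section makes the interval limit a criterion, so no decision under this plan turns on it.

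The size rests on two assumptions: the number excluded, which the documents do not give, and the 50-patient cohort. Sections 3 and 14.3 plan 30 patients in total across all three genes. Section 14.1 plans 50 plus 10, and the accrual figures in Section 14.3 (48 months at 1.25 per month) also give 60. These totals need reconciling, and the illustration would change with them.

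**What to change.** State the following in both Section 10.1.1 and Section 14.1:

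- For each cohort, the response rate and its 90% exact interval use all registered patients who received at least one dose, the same population as the decision rules.
- A patient with no post-baseline tumor assessment, for whatever reason, counts as a non-responder.
- The rate in the Section 10.1.1 evaluable set is reported as a labelled sensitivity analysis.

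Because untreated registrations are cancelled, this agrees with the registered patients of Section 14.1 and leaves the decision rules as they are. The cost is one paragraph of wording and no extra data. The reported response rate may be slightly lower.
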